10.4.4 Prior, Maintained and Concomitant Medications

Previous medications will be summarized by treatment and overall, while maintained and concomitant medications will be summarized by treatment (for the assignment of medications to a category, see section 7.2.5).

All previous, maintained and concomitant medications will be presented in the tables and the listings.

Post-treatment medications will be only presented in a listing.

Previous, maintained and concomitant medications will be summarized on the ITT population according to Anatomical Main Group (1st level of ATC), Therapeutic Subgroup (2nd level of ATC), Chemical Subgroup (4th level of ATC) and preferred name.

Absolute counts (n) and percentages (%) will be presented for the number of subjects taking at least one medication, and per Anatomical Main Group and per Therapeutic Subgroup within Anatomical Main Group and per Chemical Subgroup within Therapeutic Subgroup, for the Safety and ITT populations. Percentages will be based on the number of subjects in the population.

10.5 Study drug / Investigational Medicinal Product

10.5.1 Background medication

Daily dose of previous ICS treatment for Asthma will be summarized by summary statistics and absolute counts (n) of subjects according to the dose category (Low Daily Dose and Medium Daily Dose), and the number of morning and evening puffs that the subject was instructed to take, both for QVAR 40 µg and QVAR 80 µg for ITT population. The clinically

comparable dose assigned will also be described categorically (Low Daily Dose, Medium Daily Dose).

Exposure and compliance will be summarized by summary statistics and absolute counts (n) and percentages (%) by the treatment that the subject will be randomized to and overall during the Run-in Period for the ITT populations. In addition, the number and percentage of subjects with the following compliance categories: satisfactory (65% - 135%) and unsatisfactory (<65%; >135%) levels of compliance and following compliance categories ([0%-10%], (10%-20%], (20%-30%], (30%-40%], (40%-50%], (50%-60%], (60%-70%], (70%-80%], (80%-90%], (90%-100%], (100%-110%], (110%-120%], (120%-130%], (130%-140%], >140%) to the background medication will be summarized by treatment and overall during the Run-in Period.

10.5.2 Study drug

Treatment exposure and compliance during the Treatment Period will be summarized by summary statistics and absolute counts (n) by treatment using the ITT and Safety populations. In addition the number and percentage of subjects with satisfactory (65% - 135%) and unsatisfactory (<65%; >135%) levels of compliance to the study drug will be summarized by treatment. The summary will be repeated by the following compliance categories ([0%-10%], (10%-20%], (20%-30%], (30%-40%], (40%-50%], (50%-60%], (60%-70%], (70%-80%], (80%-90%], (90%-100%], (100%-110%], (110%-120%], (120%-130%], (130%-140%], >140%).

10.5.3 Compliance with the use of Diary

Compliance with the use of Diary in Run-in Period and Treatment period will be summarized by summary statistics and absolute counts (n) by treatment using the ITT population. In addition the number and percentage of subjects with the following compliance categories ([0%-10%], (10%-20%], (20%-30%], (30%-40%], (40%-50%], (50%-60%], (60%-70%], (70%-80%], (80%-90%], (90%-100%]) will be summarized by treatment using the ITT population.

10.6 Efficacy Results

10.6.1 Primary efficacy variable

The primary endpoint is the change from baseline in pre-dose morning FEV₁ at Week 8. The change from baseline in FEV₁ will be analyzed using a linear mixed model for repeated measurements as outlined in Section 8.2. The adjusted means in each treatment group and their corresponding 95% confidence intervals (CI), the adjusted mean difference between treatments (active – placebo) and their 95% CIs will be estimated by the model. The CIs and the p-values of the comparisons between each dose of CHF 718 pMDI and placebo at Week 8 will be adjusted for multiplicity. The adjustment will be based on the parametric simulation method by Edwards and Berry. At each dose level, the superiority of CHF 718 pMDI versus placebo will be demonstrated by a statistically significant difference (adjusted p-value < 0.05) favoring CHF 718 pMDI. In addition, the p-values for each of the factors in the model will be displayed.

The analysis will be performed using the ITT population (primary analysis) and will be repeated using the PP population.

The mean absolute FEV₁ values will be plotted over time for each of the treatment groups. These figures will be based on data from subjects in both ITT and PP populations (separate graphs for ITT and PP).

The mean change from baseline and adjusted mean change from baseline FEV₁ values will be plotted over time for each of the treatment groups. These figures will be based on data from subjects in both ITT and PP populations (separate graphs for ITT and PP).

10.6.2 Secondary efficacy variables

The secondary efficacy endpoints will be summarized using descriptive statistics with the 95% CI of the mean and will be presented by treatment for the ITT population; in addition the following analyses will be performed. There will be no adjustment for multiplicity to the CIs or the p-values for any of the secondary efficacy endpoints.

Analysis of Secondary Efficacy Variable:

- *Change from baseline in pre-dose morning FEV₁ at Week 4*

The change from baseline in pre-dose morning FEV₁ at Week 4 will be analyzed using a linear mixed model for repeated measurements as outlined in Section 8.2. The adjusted means in each treatment group with their corresponding 95% CIs, and the adjusted mean difference between treatments with their corresponding 95% CIs will be estimated by the model. In addition, the p-values for each of the factors in the model will be displayed. The mean change from baseline and adjusted mean change from baseline FEV₁ values will be plotted over time for each of the treatment groups.

- *Change from baseline in pre-dose morning FVC at Week 4 and Week 8*

The change from baseline in pre-dose morning FVC at Week 4 and Week 8 will be analyzed using a linear mixed model for repeated measurements as outlined in Section 8.2. The adjusted means in each treatment group with their corresponding 95% CIs, and the adjusted mean difference between treatments with their corresponding 95% CIs will be estimated by the model. In addition, the p-values for each of the factors in the model will be displayed. The adjusted mean change from baseline FVC values will be plotted over time for each of the treatment groups.

- *Change from baseline in ACQ-7 score at Week 4 and Week 8*

The change from baseline in ACQ-7 score at Week 4 and Week 8 will be analyzed using a linear mixed model for repeated measurements as outlined in Section 8.2. The adjusted means in each treatment group with their corresponding 95% CIs, and the adjusted mean difference between treatments with their corresponding 95% CIs will be estimated by the model. In addition, the p-values for each of the factors in the model will be displayed. The adjusted mean change from baseline in ACQ-7 score will be plotted over time for each of the treatment groups.

- *Change from baseline in average use of rescue medication (number of puffs/day) during inter-visit periods and entire treatment period*

The change from baseline to each inter-visit period and to the entire treatment period in the average use of rescue medication will be analyzed using a linear mixed model for repeated measurements as outlined in Section 8.2. See Section 7.1 for the definition of the inter-visit periods. The adjusted means in each treatment group with their corresponding 95% CIs, and the adjusted mean difference between treatments with their corresponding 95% CIs will be

estimated by the model. In addition, the p-values for each of the factors in the model will be displayed. The adjusted mean change from baseline in use of rescue medication will be plotted over time for each of the treatment groups.

- *Change from baseline in percentage of rescue medication-free days during inter-visit periods and entire treatment period*

The change from baseline to each inter-visit period and to the entire treatment period in the percentage of rescue medication-free days will be analyzed using a linear mixed model for repeated measurements as outlined in Section 8.2. See Section 7.1 for the definition of the inter-visit periods. The adjusted means in each treatment group with their corresponding 95% CIs, and the adjusted mean difference between treatments with their corresponding 95% CIs will be estimated by the model. In addition, the p-values for each of the factors in the model will be displayed. The adjusted mean change from baseline in percentage of rescue medication free days will be plotted over time for each of the treatment groups.

- *Change from baseline in daily asthma symptoms scores during inter-visit periods and entire treatment period*

The change from baseline to each inter-visit period and to the entire treatment period in daily asthma symptoms score will be analyzed separately for morning and evening and also as a total (considering both morning and evening) using a linear mixed model for repeated measurements as outlined in Section 8.2. See Section 7.1 for the definition of inter-visit periods. The adjusted means in each treatment group with their corresponding 95% CIs, and the adjusted mean difference between treatments with their corresponding 95% CIs will be estimated by the model. In addition, the p-values for each of the factors in the model will be displayed. The adjusted mean change from baseline in daily asthma symptoms scores will be plotted over time for each of the treatment groups.

- *Change from baseline in percentage of asthma symptoms-free days during inter-visit periods and entire treatment period*

The change from baseline to each inter-visit period and to the entire treatment period in percentage of asthma symptoms-free days will be analyzed using a linear mixed model for repeated measurements as outlined in Section 8.2. See Section 7.1 for the definition of inter-visit periods. The adjusted means in each treatment group with their corresponding 95% CIs, and the adjusted mean difference between treatments with their corresponding 95% CIs will be estimated by the model. In addition, the p-values for each of the factors in the model will be displayed. The adjusted mean change from baseline in percentage of asthma symptoms-free days will be plotted over time for each of the treatment groups.

- *Change from baseline in percentage of asthma control days during inter-visit periods and entire treatment period*

The change from baseline to each inter-visit period and to the entire treatment period in percentage of asthma control days will be analyzed using a linear mixed model for repeated measurements as outlined in Section 8.2. See Section 7.1 for the definition of inter-visit periods. The adjusted means in each treatment group with their corresponding 95% CIs, and the adjusted mean difference between treatments with their corresponding 95% CIs will be estimated by the

model. In addition, the p-values for each of the factors in the model will be displayed. The adjusted mean change from baseline in percentage of asthma control days will be plotted over time for each of the treatment groups.

- *Change from baseline in morning and evening pre-dose PEF during inter-visit periods and entire treatment period*

The change from baseline to each inter-visit period and to the entire treatment period in morning and evening pre-dose PEF will be analyzed using a linear mixed model for repeated measurements as outlined in Section 8.2. See Section 7.1 for the definition of inter-visit periods. The adjusted means in each treatment group with their corresponding 95% CIs, and the adjusted mean difference between treatments with their corresponding 95% CIs will be estimated by the model. In addition, the p-values for each of the factors in the model will be displayed.

10.7 Safety Analyses

All safety analyses described below will be performed on the Safety population.

10.7.1 Adverse Events

As defined in the protocol, all AEs starting on or after the date of first study drug intake will be classified as a TEAE. Only TEAEs will be included in the tables. AE onset date will be taken into account when assigning AEs as *treatment emergent*. Pre-treatment AEs (AE onset date < date of first randomized study drug intake) and post-study AEs (AE onset date > date of completion/discontinuation) will be included in the subject listings, and flagged, but will be excluded from other summaries.

The number of TEAEs, serious TEAEs, ADRs, serious ADRs, severe TEAEs, TEAEs leading to study drug discontinuation and TEAEs leading to death, and the number and the percentage of subjects experiencing TEAEs, ADRs, serious TEAEs, serious ADRs, severe TEAEs, TEAEs leading to study drug discontinuation and TEAEs leading to death will be summarized by treatment and overall.

The number and percentage of subjects with at least one AE and the number of AEs will be presented by SOC and PT by treatment and overall for treatment-emergent AEs, ADRs, serious TEAEs, serious ADRs, severe TEAEs, TEAEs leading to study drug discontinuation and TEAEs leading to death.

Subjects who have multiple events in the same system organ class (SOC) and preferred term (PT) will be counted only once in the subject counts.

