	
statistically significant difference (adjusted p-value < 0.05) favoring CHF 718 pMDI. All the other comparisons between treatments will be performed as secondary efficacy analyses with no multiplicity adjustment.
 
Secondary efficacy variables
 
No multiplicity adjustment will be performed in the secondary efficacy analyses.
 
• For change from baseline in pre-dose morning FEV₁ at Week 4, the adjusted means in each treatment group and the adjusted mean differences between treatments at Week 4 will be estimated with their 95% CIs and p-values by the same model used for the primary efficacy analysis.• Change from baseline in pre-dose morning FVC at Week 4 and Week 8 will be analyzed using a similar model as the one used for the primary efficacy analysis.• Change from baseline in ACQ-7 score at Week 4 and Week 8 will be analyzed using a similar model as the one used for the primary efficacy analysis.• Change from baseline to each inter-visit period in average use of rescue medication, in percentage of rescue medication-free days, in daily asthma symptoms scores, in percentage of asthma symptoms-free days, in percentage of asthma control days and in morning and evening pre-dose PEF will be analyzed using a similar model as the one used for the primary efficacy analysis. The inter-visit period will be considered instead of visit in the model. Comparison between treatments over the entire treatment period will also be derived from this model. 
Safety variables
 
Adverse Events
 
All adverse events starting on or after the time of first study drug intake will be classified as Treatment Emergent Adverse Events (TEAEs). Any adverse event started after the informed consent signature and before the time of first study drug intake will be classified as pre-treatment adverse event. Pre-treatment adverse events will be listed only.
 
The number of TEAEs and the number and percentage of subjects who experienced at least one TEAE will be presented by treatment for all AEs, ADRs, serious AEs, serious ADRs, severe AEs, AEs leading to study discontinuation and AEs leading to death. Summaries will be presented overall and by system organ class and preferred term based on the MedDRA dictionary.
 
Vital signs
 
Vital signs (systolic and diastolic blood pressure) and their changes from baseline (Visit 2) will be summarized by treatment using descriptive statistics and the 95% CI of the mean.

--	--

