7.1.3 Visit 2 (Randomization/ Start of Treatment Period /Week 0)

The Visit 2 will start in the morning (before 9:00 am).

If caffeine has been ingested, or rescue albuterol has been inhaled in the previous 6 hours, or the washout for non-permitted medications has not been respected, or the run-in ICS medication (QVAR[®]) has been taken in the morning of the visit (before spirometry), the visit needs to be re-scheduled to take place within 2 days. Only one re-scheduling is allowed. If any of these relevant

washouts is not respected again on the morning of the re-scheduled visit, the subject will be discontinued and recorded as a screen failure in the IRT and eCRF.

The following pre-dose procedures will be performed:

- The ACQ questionnaire will be completed.
- Vitals signs [systolic (SBP) and diastolic (DBP) blood pressure] will be measured before spirometry, bronchodilator, and study drug administration, after 5 minutes of rest, in resting position (see [section 7.2.3](#)).
- A 12-lead ECG will be performed before spirometry, bronchodilator, and study drug administration, after 5 minutes of rest (see [section 7.2.5](#)).
- The investigator will check in the electronic diary portal whether subject has been transmitting data daily since screening. **In case of lack of compliance, instructions on how to use it will be provided again to the subject** (see [section 7.2.12](#)).
- Changes of concomitant medications being taken by the subject will be recorded. In case of intake of any non-permitted concomitant medication, the subject will be withdrawn from the study and recorded as a screen failure in the IRT. (see [section 5.2](#)).
- A full physical examination will be performed including assessment for oral candidiasis.
- A urine pregnancy test in women with childbearing potential will be performed.
- 24-hour urine sample will be processed for 24-hour urine cortisol and creatinine (see [section 7.2.8](#)).
- The occurrence of other adverse events will be checked and recorded if any.
- The proper use of pressurized metered dose inhaler will be checked and subject will be retrained to the usage of the pMDI using the Training kit previously assigned at V1 (see [section 6.2.4](#)).
- Run-in ICS medication (QVAR®) will be collected and disposed of per the study sponsor's instructions.

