12.3.6 Safety variables

Adverse Events

All adverse events starting on or after the time of first study drug intake will be classified as Treatment Emergent Adverse Events (TEAEs). Any adverse event started after the informed consent signature and before the time of first study drug intake will be classified as pre-treatment adverse event. Pre-treatment adverse events will be listed only.

The number of TEAEs and the number and percentage of subjects who experienced at least one TEAE will be presented by treatment for all AEs, ADRs, serious AEs, serious ADRs, severe AEs, AEs leading to study discontinuation and AEs leading to death. Summaries will be presented overall and by system organ class and preferred term based on the MedDRA dictionary.

Vital signs

Vital signs (systolic and diastolic blood pressure) and their changes from baseline (Visit 2) will be summarized by treatment using descriptive statistics and the 95% CI of the mean.

ECG

12-lead ECG parameters (HR, QTcF, QRS and PR) and their changes from baseline (Visit 2) will be summarized by treatment using descriptive statistics and the CI of the mean (95% CI for absolute values and 90% CI for the changes from baseline).

The number and the percentage of subjects with a:

- QTcF >450ms (males only), >470ms (females only), >480ms (males only) and >500ms
- change from baseline (Visit 2) in QTcF >30ms and >60ms
- at post-baseline visit will be presented by treatment group.

Laboratory parameters

Shift tables from screening to the end of treatment, based on normal ranges, will be presented by treatment group for the laboratory parameters.

Mean change from baseline (Visit 2) to the end of treatment in 24-h urinary free cortisol and creatinine will be calculated with its 95% CI by treatment group.

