Inter-visit periods will be used in the analysis of the average number of rescue medication, the percentage of rescue medication-free days, the percentage of asthma symptoms-free days and of asthma control day, the daily asthma symptoms scores and the morning and evening average pre-dose PEF. The periods used in these analyses are:

- Run-in Period: The Run-In Period starts at Visit 1 and runs through morning assessment of the date of Start of the Randomized Treatment Period.

- Inter-visit Period 1: Inter-visit Period 1 starts on the evening assessment of the date of the Start of the Randomized Treatment Period and runs through the morning assessment on the date of Visit 3. If the subject withdraws prematurely after Visit 2 and before Visit 3 any value collected from Visit 2 until the End of the Randomized Treatment Period will be considered for the Inter-visit Period 1. By default Inter-visit Period 2 is missing.
- Inter-visit Period 2: Inter-visit Period 2 starts on the evening assessment of the day the subject returns to the clinic at Visit 3 and runs through the morning assessment of the date of Visit 4.

If the subject withdraws prematurely after Visit 3 and before Visit 4 any value collected from Visit 3 until the End of the Randomized Treatment Period will be considered for the Inter-visit Period 2.

Date of first/last study drug intake

Date of first randomized study drug intake is derived as the minimum of 'Date/Time of administration' between the 4 inhalations (puffs) of the Morning Dose collected on the 'Study drug administration at the clinic' eCRF page. While subjects randomized to open-label QVAR® will only receive 1 inhaler, patients are required to take 2 inhalations of the content of 1 inhaler on site, the morning of Visit 2. For these patients, no minimum is required, since only 1 time is recorded.

Note: The date and time of drug administration at each visit are mandatory variables to be reported in the CRF; no missing or partial data can be accepted. Only CRF data will be considered for the date of first randomized study drug intake.

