7.2.11 Safety Assessments

There are 5 sets of safety variables identified in the protocol. A description of each variable, and the timing of the recording of the information is presented below.

- 1: Treatment Emergent Adverse Events (TEAEs)

Three categories of AEs will be presented: Pre-Treatment, Treatment Emergent, and Post-Study. An AE will be classified as:

- pre-treatment AE: if AE starts before the first randomized study medication intake (AE onset date < date of first randomized study medication intake).
- Treatment emergent AEs (TEAEs): all adverse events starting on or after the first study drug intake, up to study completion/discontinuation. TEAEs are defined as AEs with date of first randomized study drug intake \leq AE onset date \leq date of study completion/discontinuation.
- post-study AE: if AE starts after the date of completion/discontinuation (AE onset date > date of completion/discontinuation).

Additional variables to define an adverse event include the following:

- Serious AE (SAE) is defined as any AE that has the question “Is the AE serious?” marked as “Yes” on the eCRF.
- ADR is defined as any AE that has the question “Is the AE Related to Study Drug?” marked as “Yes” on the eCRF.
- Serious ADR is defined as any ADR that are also SAE
- *Severe AE*, defined as any AE that has intensity marked as “Severe” on the eCRF.
- *AE leading to study drug discontinuation*, defined as a TEAE where the action taken on the eCRF is marked as “Drug withdrawn”.
- *AE leading to death*, defined as a TEAE where the outcome is marked as “Fatal” on the eCRF.
- *Relative day of AE onset*, defined as the AE onset date – Date of first study drug intake + 1 if the AE onset date is greater or equal to date of first study drug intake. For pre-treatment AEs, the relative day is defined as the AE onset date – Date of first study drug intake. Relative day will not be calculated in case of partial/missing date of AE onset.
- *Duration of AE*, defined as the AE end date – AE onset date + 1 when the AE is resolved. If the AE is not resolved, the duration is defined as study completion date – AE onset date + 1 and the duration will be reported as “>x” in the listing. AE duration will not be calculated in the case of a partial/missing date of AE onset.

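### The SAP splits adverse events at the date of first intake and credits the protocol, but the protocol splits them at the time, so Day 1 pre-dose events are tabulated as treatment-emergent

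*SAP*

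**What the plan says.** Protocol 12.3.6 sets the boundary by clock: "Any adverse event started after the informed consent signature and before the time of first study drug intake will be classified as pre-treatment adverse event". Such events go into a listing and not into the tables. The synopsis has the same rule from the other side, describing treatment-emergent events as "All adverse events starting on or after the time of first study drug intake".

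SAP 10.7.1 says: "As defined in the protocol, all AEs starting on or after the date of first study drug intake will be classified as a TEAE". It adds that onset date is what counts in the assignment and that only treatment-emergent events are tabulated. In SAP 7.2.11 the pre-treatment formula is "AE onset date < date of first randomized study medication intake", and the treatment-emergent formula likewise compares calendar dates. The prose introducing those two formulas refers to the first intake itself, without mentioning its date.

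SAP 3.8 reports no change from the protocol. SAP 7.1 notes that "The date and time of drug administration at each visit are mandatory variables to be reported in the CRF".

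**The concern.** The two documents agree except for events that begin on the calendar day of the first dose but before that dose. This window exists by design. Protocol 7.1.3 schedules vital signs, a 12-lead ECG, a physical examination and spirometry 45 and 15 minutes pre-dose, all on the morning of Visit 2 and before randomized treatment starts. The same pre-dose list includes an adverse event check: "The occurrence of other adverse events will be checked and recorded if any". Under Protocol 10.8, clinically significant changes found at visits after Visit 1 are reported as adverse events.

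A subject in this window has taken only run-in medication. Under the SAP rule, an event starting then is counted against the randomized arm and is absent from the pre-treatment listing, where the protocol places it. Every treatment-emergent table rests on this definition. The SAP presents its version as the protocol's own, so a reader of the study report would not know that it differs.

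**Working it through.** There is no stated figure to reproduce. The check compares the two rules at the boundary and then sizes the difference.

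**Rules compared**

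- Protocol 12.3.6 and synopsis: treatment-emergent if onset date and time ≥ first-dose date and time.
- SAP 7.2.11 formulas and SAP 10.7.1: treatment-emergent if onset date ≥ first-dose date.

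**Boundary test.** The first dose is assumed at 09:30 on Day 1. Protocol 7.1.3 requires it in clinic before 10 am, and SAP 7.1 defines Day 1 as the date of that dose.

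| Onset | Protocol rule | SAP rule |
|---|---|---|
| Day -1, 22:00 | pre-treatment | pre-treatment |
| Day 1, 07:00 | pre-treatment | treatment-emergent |
| Day 1, 08:45 | pre-treatment | treatment-emergent |
| Day 1, 09:30 | treatment-emergent | treatment-emergent |
| Day 1, 12:00 | treatment-emergent | treatment-emergent |

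Only the two pre-dose onsets on Day 1 differ.

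**Does another SAP rule catch these events?** No. The worst-case allocation in SAP 7.2.11 applies when the adverse event date is missing or incomplete. A complete Day 1 date is outside it.

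**Size.** Assume a constant event rate, *h* hours from midnight to the first dose and *D* days of observation after it. The share of tabulated events that the protocol would call pre-treatment is

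share = (h/24) / (D + h/24).

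Inputs:

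- *h* = 8 to 10. This is an assumption; 10 is the upper limit because dosing is before 10 am.
- *D* = 56 (8 weeks × 7, to Visit 4) to 63 (9 weeks × 7, to the follow-up call).

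| h | D = 56 | D = 63 |
|---|---|---|
| 8 | 0.59% | 0.53% |
| 9 | 0.67% | 0.59% |
| 10 | 0.74% | 0.66% |

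For example, h = 10 and D = 56 gives 0.417/56.417 = 0.74%. The range is about 0.5% to 0.7%.

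**The case against.** The strongest reply is that the fix may have little to act on. The documents show that dose time is collected but not that onset time is. The SAP's category, relative-day and duration derivations all use onset date. If only dates exist, a Day 1 onset cannot be ordered against the dose without a query, and treating it as treatment-emergent is the conservative choice. This stands in part: a date rule is a defensible fallback. It does not excuse crediting the rule to the protocol or leaving it out of SAP 3.8. A before/after query could still move events between the tables and the pre-treatment listing, so more than wording is involved.

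The SAP cites protocol version 3.0, whereas the supplied protocol refers to version 4.0 in its re-screening text. Version 3.0 may have been worded differently, but the SAP would still need reconciling with the protocol supplied.

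Four stronger readings are tempting, and the documents do not support them:

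- **That pre-dose events become adverse drug reactions.** Under SAP 7.2.11, that status requires the investigator to mark the event as related. Protocol 10.4 asks the investigator to consider the timing of intake and onset. The date rule does not supply a relatedness answer.
- **That the Visit 2 adverse event check concentrates misclassified events.** Classification follows onset, not detection. Events picked up at that check with onset before Day 1 are pre-treatment under both rules.
- **That every abnormal Visit 2 finding reaches the tables.** Oral candidiasis, QTcF above the limits and ECG abnormalities posing a safety problem are exclusions rechecked at Visit 2. A severe exacerbation after Visit 1 leads to withdrawal. Subjects removed before dosing are outside the Safety population.
- **That arm comparisons are biased.** A pre-dose event cannot be caused by the assigned arm, so the expected addition is equal across arms. It leaves absolute differences unbiased and attenuates ratios slightly. SAP 10.7.1 plans counts and percentages and no between-arm test. The events also remain visible in the treatment-emergent listing.

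**Conclusion.** The point holds and is minor. The SAP replaces the protocol's time boundary with a date boundary, attributes this to the protocol and declares no change; its 7.2.11 prose and formulas also disagree. The result is that a Day 1 pre-dose event in a subject who goes on to be randomized and dosed is tabulated instead of being listed only as pre-treatment.

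The estimate of about 0.5% to 0.7% of treatment-emergent events rests on uniform onsets and on the assumed window and observation lengths. It could be higher if onsets, as opposed to detections, cluster around the Visit 2 procedures, but the documents give no event counts with which to judge that. The rule adds background events in all five arms. A reader might infer a safety signal favouring or penalising a particular dose; nothing in the documents supports that.

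**What to change.** In SAP 7.2.11 and 10.7.1, add a rule for adverse events whose onset date equals the date of first intake:

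1. Compare onset time with the recorded first-dose time.
2. If the eCRF does not hold onset time, query the site on whether the event began before or after the first dose.
3. Class the event as pre-treatment if it began before the dose.
4. Class it as treatment-emergent if the timing remains unknown, in line with the SAP's existing worst-case ordering.

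Align the 7.2.11 formulas with their prose, and correct the 10.7.1 sentence that attributes the date rule to the protocol. If the sponsor prefers to keep a date convention, record it in SAP 3.8 as a difference from Protocol 12.3.6.

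The cost is a few lines of SAP text and programming, plus a small number of queries limited to Day 1 onsets, to be completed before database lock and unblinding.
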